4.1 OVERVIEW OF STUDY DESIGN/INTERVENTION

4.2 Design

The proposed study is a randomized controlled trial study. The primary aim of this study is to assess the feasibility of an automated geriatric co-management program for perioperative management of patients with solid mass or nodule who present to MSKCC Surgery Service clinics, and being considered for surgery.

Secondary aims are to collect preliminary data on its impact on postoperative adverse surgical outcomes, and functional recovery compared to in-person geriatric co-management.

The first visit (surgery clinics when patients are being considered for surgical resection of their solid mass or nodule suspicious for cancer): In surgery clinics, all patients complete the eRFA as a routine care.

Inclusion criteria are: 1) solid mass or nodule suspicious for cancer, 2) aged 65 or older, 3) being considered for surgical resection of the solid mass or nodule with anticipated hospital length of stay of at least two days, 4) completed eRFA.

Exclusion criteria: 1) unable to read or comprehend English, 2) not having a completed eRFA within the two months of undergoing surgery, 3) being discharged in one day or earlier from the hospital.

Note) To avoid excluding patients based on item 2, patients have to complete another eRFA within two months of surgery.

Following patients' consent to participate in the study, patients will also complete a 4-Meter walk test (4MVMT)[31]. Their sociodemographic characteristics will also be recorded.

Subsequently, they will be randomized either to in-person geriatric co-management or the automated geriatric co-management program, using MSKCC's Clinical Research Database, a secure randomization system ensuring full allocation concealment.

The automated geriatric co-management program group: Through literature review, consideration of American College of Surgeons and American Geriatrics Society recommendation[32], and our years of collective experience for postoperative care for older adults with cancer, we have developed perioperative geriatric recommendations for each of the 12 eRFA impairments and comorbid conditions (appendix 1).

Following completion of the eRFA, the summary of impairments as well as the recommendations generated by the study team (hard-copy or email) will be provided in real-time to the thoracic surgery team for their attention. A sample is provided below. In this case, patient has impairments in various domains that ranges from KPS to number of medications.

[eRFA Summary](#)

Global recommendation: If 3 or more impairments are listed in the summary below, consider referral to geriatrics.
T = Threshold | **P** = Percentile | **PS** = Patient Score

KPS  More Information:	T: ≤ 80	P: 37%	PS: 60.
ADL  More Information:	T: < 14	P: 52%	PS: 12.
iADL  More Information:	T: < 16	P: 45%	PS: 13.
Timed Up and Go Test  More Information:	T: ≥ 10 seconds	P: 36%	PS: 10-19 seconds.
Social Support  More Information:	T: ≤ 16	P: 43%	PS: 16.
Limited Social Activity  More Information:	T: ≥ 8	P: 50%	PS: 12.
Weight Change  More Information:	T: 10 pound loss or more	P: 16%	PS: 10-20.
Distress Level  More Information:	T: ≥ 4	P: 55%	PS: 7.
Number of Medications  More Information:	T: ≥ 5	P: 45%	PS: More than ten.

Subsequently, the research staff member clicks on various impairments and would be able to view and print the recommendations for each impairment. For example, the following are the recommendations for a Timed Up and Go test impairment.

Timed Up and Go Test **T:** ≥ 10 seconds **P:** 36% **PS:** 10-19 seconds.

[More Information:](#)

[Pre/Postop Recommendation:](#)

- A- Consider consultation with physical therapy and occupational therapists.
- B- Encourage use of appropriate assistive devices.
- C- Encourage resistance exercises such as repeated chair stand in the preoperative period.
- D- Consider use of stationary bike or bike pedals in the preoperative period.

[Medical Recommendation:](#)

[Education:](#)

[Supportive Services:](#)

A copy of the recommendations will be available in EMR. After preoperative clearance by patients' primary care providers, general internal medicine service, or other services such as cardiology, patients will undergo surgery. The geriatrics service will see patients before or after surgery if the consult is requested by the surgery service. The automated co-management program is not expected to lengthen the patients' first visits.

The in-person geriatric co-management group. Patients randomized to the in-person geriatric management will be seen by MSKCC's geriatrics service for preoperative evaluation. The evaluation may be done either in clinic or via telemedicine. Based on the eRFA results and other issues found during the preoperative evaluation, geriatricians will make recommendations to be executed in the postoperative period. Patients are then co-managed by the geriatrics service during hospital course after surgery. The geriatrics service sees these patients for at least 2 postoperative days, if deemed clinically necessary by the geriatrician. During the inpatient hospital course, the geriatrics service will ensure the execution of preoperative recommendations and will discuss with the surgical team, who will act as a primary team, any additional recommendation in order to improve postoperative care.[33]

The 2nd study visit (outpatient follow-up visit by the surgery team, usually within 2 weeks after hospital discharge): During this meeting, once again patients complete the eRFA as a routine care, and perform 4MWT. The 2nd visit may also be conducted via telemedicine, depending on patient preference.

Patients' follow up continues until day 30 after surgery with hospital length of stay of at least two days in which the surgical adverse events (surgical complications grade 2+, disposition to any place other than home, length of stay, and readmission), surgery characteristics, cancer characteristics, and preoperative lab results will be collected by the study team.

Patients go off-study either at the 2nd study visit or 30 days after surgery, whichever happens later.

4.3 Intervention

The automated geriatric co-management program group: Through literature review, consideration of American College of Surgeons and American Geriatrics Society recommendation[27], and our years of collective experience for postoperative care for older adults with cancer, we have developed perioperative geriatric recommendations for each of 12 eRFA impairments and comorbid conditions (appendix 1)

Following completion of the eRFA, the summary of impairments as well as the recommendations generated by the study team (hard-copy or email) will be provided in real-time to the surgery team for their attention.

It will be up to the surgeons and the surgical team whether they follow the recommendations or not. The rate of follow up of the recommendation is the primary aim of this study.

A sample is provided below. In this case, patient has impairments in various domains

that ranges from KPS to number of medications.

eRFA Summary

Global recommendation: If 3 or more impairments are listed in the summary below, consider referral to geriatrics.
T = Threshold | **P** = Percentile | **PS** = Patient Score

KPS  More Information:	T: ≤ 80	P: 37%	PS: 60.
ADL  More Information:	T: < 14	P: 52%	PS: 12.
iADL  More Information:	T: < 16	P: 45%	PS: 13.
Timed Up and Go Test  More Information:	T: ≥ 10 seconds	P: 36%	PS: 10-19 seconds.
Social Support  More Information:	T: ≤ 16	P: 43%	PS: 16.
Limited Social Activity  More Information:	T: ≥ 8	P: 50%	PS: 12.
Weight Change  More Information:	T: 10 pound loss or more	P: 16%	PS: 10-20.
Distress Level  More Information:	T: ≥ 4	P: 55%	PS: 7.
Number of Medications  More Information:	T: ≥ 5	P: 45%	PS: More than ten.

Subsequently, the research staff member clicks on various impairments and would be able to view and print the recommendations for each impairment. For example, the following are the recommendations for a Timed Up and Go test impairment.

Timed Up and Go Test **T:** ≥ 10 seconds **P:** 36% **PS:** 10-19 seconds.

More Information:

Pre/Postop Recommendation:

- A- Consider consultation with physical therapy and occupational therapists.
- B- Encourage use of appropriate assistive devices.
- C- Encourage resistance exercises such as repeated chair stand in the preoperative period.
- D- Consider use of stationary bike or bike pedals in the preoperative period.

Medical Recommendation:

Education:

Supportive Services:

A copy of the recommendations will be available in EMR. After preoperative clearance by patients' primary care providers, general internal medicine service, or other services such as cardiology, patients will undergo surgery. The geriatrics service will see patients before or after surgery if the consult is requested by the surgery service. The automated co-management program is not expected to lengthen the patients' first visits.

5.1 CRITERIAFOR SUBJECT ELIGIBILITY

Patients who present to MSKCC surgery clinics for consideration of surgery for their solid mass or nodule will be selected.

5.2 Subject Inclusion Criteria

- 1) Solid mass or nodule/lesion suspicious for cancer,
- 2) Aged 65 or older,
- 3) Being considered for surgical resection of solid mass / nodule/lesion with anticipated hospital length of stay of at least two days,
- 4) Completed the eRFA per routine care

5.3 Subject Exclusion Criteria

- 1) Unable to read or comprehend English
- 2) Not having a completed eRFA within the two months of undergoing surgery

Note) To avoid excluding patients based on item 2, patients have to complete another eRFA within two months of surgery.

- 3) Being discharged in one day or earlier from the hospital.

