7.1 ASSESSMENT/EVALUATION PLAN

Assessment and Measurement Instruments:

In this study, the data will be collected using the following instruments and measurements methods:

- Electronic Medical Record review:

- 1- For patients in the intervention group (automated geriatric co-management), we will assess the percentage of recommendations that were followed by the surgery team. For example, if automated geriatric co-management recommends consultation with physical therapy perioperatively, we will assess whether the consult has been obtained.
- 2- For patients in both groups, we will assess the adverse surgical events by day 30 following surgery. Adverse surgical event is a composite of surgical complications grade 2 or higher, mortality after surgery, or discharge to any place other than home, or prolonged length of stay (defined as length of stay longer than 75% of the cohort who underwent the same surgical procedure), or readmission to the hospital within 30 days from surgery.

MSKCC's secondary surgical events database in the EMR has been shown to accurately record major postoperative complications within the 30 days after surgery[34].

- 3- to assess sociodemographic characteristics (age, gender, ethnicity),
- 4- to assess routine preoperative blood work (complete blood cell counts, chemistry panel).
- 5- To assess cancer characteristics (stage, receipt and type of neoadjuvant treatment)

- 6-** To assess surgical characteristics (type of surgery: minimally invasive vs open, duration of surgery, intraoperative blood loss, and American Society of Anesthesiologist Physical Status classification)
- **Four Meter Walk Test:** In order to assess functional recovery, the 4-meter walk test will be performed. In the 4-meter walk test, the time that it takes patients to walk 4 meters in their usual pace will be recorded in seconds by the clinical research staff. (This portion will be skipped for patients being seen via telemedicine.)

Assessment and Evaluation Plan

Patients will be screened for study eligibility at the time of attending their surgery appointment at MSKCC for consideration of surgery. The inclusion and exclusion criteria will be reviewed by the clinical research staff firstly to confirm the patients' eligibility status. Once eligibility has been determined and informed consent has been obtained, patients will undergo baseline assessments and subsequently randomization will occur.

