10.1 CRITERIA FOR REMOVAL FROM STUDY

Patients will have completed their participation in this study after the 30-day post-surgery follow-up or the 2nd study visit, whichever occurs later, and will be considered off-study.

Participants will be removed from the study if:

- ✓ He/she chooses to withdraw consent for continued participation at any time
- ✓ The participant reports intolerable distress due to study participation
- ✓ He/she becomes ineligible for study participation as designated by the inclusion/exclusion criteria

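### Exclusion 3 depends on actual discharge and so acts after randomization; the plan does not say whether short-stay patients stay in the Aim 2 comparison, and it defines the Aim 2 composite in two ways on mortality

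*Combined protocol and SAP*

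**What the plan says.** **Entry and exclusion.** Section 5.2 admits patients considered for resection "with anticipated hospital length of stay of at least two days". This is a judgment available before randomization. Exclusion 3 in section 5.3 (repeated in sections 1.0 and 4.2) instead uses the event itself: "Being discharged in one day or earlier from the hospital".

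**Timing.** Section 7.1 says that after eligibility and consent "patients will undergo baseline assessments and subsequently randomization will occur". Its schedule places randomization at the baseline visit, or at the pre-operative visit if two months have passed.

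**Removal and follow-up.** Section 10.1 removes a participant if "He/she becomes ineligible for study participation as designated by the inclusion/exclusion criteria". Section 4.2 says that patients' "follow up continues until day 30 after surgery with hospital length of stay of at least two days".

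**Analysis.** Section 11.0 (Secondary Aims) specifies modified intent-to-treat by assigned arm for all between-group comparisons. The only modification it states is complete case. Under Sample size it adds a sensitivity analysis with multiple imputation of missing outcomes.

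**Composite.** One component in section 7.1 is "prolonged length of stay (defined as length of stay longer than 75% of the cohort who underwent the same surgical procedure". Section 7.1 also lists mortality after surgery as a component. The definition in section 11.0 does not, and neither do the day-30 collection lists in sections 4.2 and 7.1. The table in section 9.0 has only a general adverse-events row.

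**The concern.** An exclusion that can be applied only after assignment no longer defines who enters the trial; it selects among patients already randomized. Here the selecting variable is length of stay, whose upper tail is itself an Aim 2 event. Cutting the lower tail tends to remove event-free patients, although a patient who goes home early can still be readmitted or have a grade 2 or higher complication. If the two arms lose different shares of such patients, or patients with different prognosis, the Aim 2 comparison moves without any treatment effect.

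There is a possible route to a difference. Only the in-person arm has planned inpatient geriatrics visits: "The geriatrics service sees these patients for at least 2 postoperative days, if deemed clinically necessary by the geriatrician". That is the range of stay in which exclusion 3 operates.

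On mortality, two analysts working from sections 7.1 and 11.0 could classify the same death differently.

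**Working it through.** **The plan's own figure first.** Section 11.0 gives SD 1.8, correlation 0.5 and about 95 patients per arm. Two-sided alpha 0.05 is my assumption, since none is stated for the secondary endpoints.

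- Residual SD = 1.8 × √(1 − 0.5²) = 1.559.
- SE of the difference = 1.559 × √(2/95) = 0.226.
- Power for differences of 0.5, 0.67 and 0.8 = 59.9%, 84.2% and 94.3%. The plan states 60%, 84% and 94%, so its table reproduces.

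The table allows for 5% drop-out but names no short-stay removals. If these took an assumed further 5%, 10% or 20% of each arm, n per arm would be about 90, 86 or 76, and power at 0.67 would be 82.3%, 80.2% or 75.5%. The 25% primary-aim allowance also names only no impairment (5%) and crossover (20%).

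**Bias in Aim 2.** Let P be the overall event rate, p the share removed, and r the event rate among those removed. Then the observed rate is (P − p·r)/(1 − p), with n = 95(1 − p) per arm. Only the 95 comes from the plan, where it is stated for the continuous endpoints; P, p and r are assumptions. There is no true arm difference. SEs are for an unadjusted difference of proportions.

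For P = 40% and r = 0 the observed rates are:
- p = 2%: 0.40/0.98 = 40.8%
- p = 5%: 0.40/0.95 = 42.1%
- p = 10%: 0.40/0.90 = 44.4%
- p = 15%: 0.40/0.85 = 47.1%

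| Removed, arm 1 vs arm 2 | Difference, r = 0 | SE | OR | Two-sided rejection rate | Difference, r = 20% |
|---|---|---|---|---|---|
| 5% vs 2% | 1.3 points | 7.3 | 1.05 | 5.4% | 0.6 points |
| 10% vs 5% | 2.3 points | 7.5 | 1.10 | 6.1% | 1.2 points |
| 15% vs 5% | 5.0 points | 7.6 | 1.22 | 10.0% | 2.5 points |

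- If r equals the overall 40%, every difference is 0. Equal removal with equal prognosis also gives 0.
- Equal removal with unequal prognosis does not. With 10% removed in each arm, r = 0 in one and r = 40% in the other, the rates are 44.4% and 40.0%: 4.4 points, SE 7.5.
- With 5% removed in one arm, the other must lose about 20% (r = 0) or 31% (r = 20%) before the bias reaches one SE.
- For P from 20% to 60% with r = 0, 10% vs 5% gives 1.2 to 3.5 points and 15% vs 5% gives 2.5 to 7.4 points. Only the last, at P = 60%, reaches one SE (7.2).

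**Mortality.** No arithmetic applies. Section 7.1 counts a death and section 11.0 does not name it. The documents give no death rate, so the number of patients affected cannot be estimated.

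**The case against.** **The conflict may be only apparent.** Section 10.1 governs participation. It does not say that collected data are discarded or that the patient leaves the analysis. Section 11.0 calls its set modified, and imputation could fill missing outcomes. The follow-up clause in section 4.2 can also be read as describing the intended population. A reader might infer that the plan orders short-stay patients out of the Aim 2 analysis, in flat contradiction of its intent-to-treat rule. The documents do not go that far, and this part of the objection stands. What remains is that no section says which rule governs. A patient discharged on day 1 has a known length of stay and disposition; readmission and later complications would go missing only because the rules stop follow-up. Nothing says that removed patients re-enter through imputation.

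**The two-day stay looks deliberate.** Section 11.0 bases its recruitment forecast on patients with stays of 2 days or longer. That supports the target population, which the anticipated-stay criterion already serves. It does not justify applying actual stay after assignment.

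**The route to bias is weak.** In-person inpatient visits depend on clinical judgment. The automated arm may receive geriatrics consults on request, its summary suggests considering referral at 3 or more impairments, and 20% crossover is expected. All of this stands and reduces the contrast between arms. A reader might infer that Aim 2 is biased; the documents show neither differential removal nor its direction.

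**Deaths may be captured elsewhere.** Serious adverse event reporting (section 14.3), the adverse-events row or complication grading could each record a death. No section links any of these to the composite.

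**Conclusion.** The concern holds as an unresolved inconsistency that should be settled before analysis. Exclusion 3 can act only after randomization. With sections 10.1 and 4.2 it ends participation and follow-up for short-stay patients, who are then likely to be lost from Aim 2, and section 11.0 does not say otherwise.

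The effect is probably modest. Entry on anticipated stay should keep removals few, and Aim 2 is a secondary aim meant to yield preliminary data. Under the assumed rates the spurious difference is mostly below one SE: about 1 to 5 points at a 40% event rate against roughly 7.5, and zero when removal and prognosis match across arms. These scenarios are illustrations and not a worst case: equal 10% removal with unequal prognosis gives 4.4 points, more than the 2.3 points for 10% vs 5%. The direction is unknown.

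A reader might extend the point to Aim 1. That result is a single-arm proportion, so this arm-comparison bias does not touch it; the only open question there is whether short-stay patients count among the 77.

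The mortality mismatch is plain in the text and needs no assumption, but its size cannot be estimated.

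**What to change.** 1. Keep anticipated stay of at least two days (section 5.2) as the entry criterion, and delete actual discharge as an exclusion in sections 1.0, 4.2 and 5.3.
2. State in section 10.1 and in the follow-up clause of section 4.2 that an actual stay of one day or less neither ends follow-up nor removes a patient from the Aim 2 and 3 analyses.
3. Analyze Aim 2 by assigned arm in all randomized patients who undergo surgery, and report by arm the numbers without surgery and with early discharge. Acknowledge that conditioning on surgery is itself post-randomization: only the in-person arm has a planned preoperative geriatrics evaluation, which could affect whether surgery goes ahead. The condition is hard to avoid, because every component is counted from surgery or its hospital stay.
4. State in section 11.0 whether short-stay patients count among the 77 evaluable for Aim 1. Deleting exclusion 3 would otherwise admit them by default.
5. Use one composite that includes 30-day death in sections 7.1 and 11.0, and list death in the day-30 collection in sections 4.2, 7.1 and 9.0.

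The cost is a wording amendment. Aim 2 outcomes already come from medical record review and deaths are already reportable as serious adverse events, so the extra data burden is one explicit line. The downside is slight dilution from patients who receive little postoperative co-management.

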6.0 RECRUITMENT PLAN

The patients' surgeons and nurse practitioners who will have an established medical relationship with potential participants will identify potentially eligible patients for the proposed study in advance of their consultations. Patients of both genders and all ethnicity will be considered for participation in the proposed study. Patient eligibility will be determined by the clinical research staff. A consenting professional will comprehensively go through the details of the study with patients and provide patients with time to ask questions and have them answered fully. Patients will be encouraged to take adequate time before making their decision regarding participation in the study. For those that indicate a desire to participate in the study, they will be consented by a consenting professional and the first study visit assessment will take place at that time. The surgery team will also be informed of the data they will be required to collect and document from their consultation with the patient. For patients that require more time to make their decision regarding participation, subjects may be enrolled at any time prior to their surgery. They will be informed that they will be contacted by a member of the research team in the coming days to learn of their decision.

During the initial conversation between the investigator/research staff and the patient, the patient may be asked to provide certain health information that is necessary to the recruitment and enrollment process. The investigator/research staff may also review portions of their medical records at MSKCC to further assess eligibility. They will use the information provided by the patient and/or medical record to confirm that the patient is eligible and to contact the patient regarding study enrollment. If the patient turns out to be ineligible for the

research study, the research staff will destroy all information collected on the patient during the initial conversation and medical records review, except for any information that must be maintained for screening log purposes or processes.

For patients that are not interested in taking part in the proposed study, an expression of thanks will be offered for the opportunity to discuss potential study enrolment with them. Patients will be asked if they would be willing to provide their primary reason for declining participation. They will be informed that this answer will be anonymously recorded for the purpose of understanding factors that influence patient decisions regarding participation in the study. If a patient declines to offer a reason this will be recorded as "patient declined to offer a reason for non-participation in the study".

Payment to Participants Study participants will not receive any payment for their participation in the proposed study.

